7. INTERFERENCE WITH DAILY ACTIVITIES

a. In the **last week**, did the operation prevent you from carrying out **work/housework** and other **daily activities**?

*(Please mark **one** box)*

No, not at all.

I could continue with my work, but my work suffered.

Yes, for 1 day.

Yes, for 2–6 days.

Yes, for 7 days.

b. In the **last week**, have your **leisure activities** been affected by your operation?

(including sports, hobbies and social life)

*(Please mark **one** box)*

Not affected by the operation.

Mildly affected by the operation.

Moderately affected by the operation.

Severely affected by the operation.

The operation prevented any social life at all.

c. Thinking of the **last week**, how badly did the pain affect your **life**?

*(Please mark **one** box)*

Not at all Slightly Moderately Severely

Appendix 4: Neurological Assessment

A neurological assessment will be conducted at baseline (prior to study drug administration); 15 minutes, 30 minutes, 1, 2, 4, 8, 12, 18, 24, 30, 36, 42, 48, 54, 60, 66, 72, 84, and 96 hours after the beginning of study drug administration; and on Day 10.

The examination will include the subject's orientation.

- Is the subject oriented? Yes No

If the subject is not oriented, the event should be recorded as an AE.

Additionally, the subject will be asked the following questions:

- Do you have numbness of the lips, the tongue, or around the mouth?
 Yes No
- Do you have a metallic taste in your mouth?
 Yes No
- Are you having problems with your hearing not related to the use of a hearing aid?
 Yes No
- Are you having problems with your vision not related to the use of eye glasses?
 Yes No
- Are your muscles twitching?
 Yes No

If the subject answers "yes" to any of these questions, the event should be recorded as an AE.

1. LIST OF ABBREVIATIONS

| | |
|-----------|--|
| AE | Adverse Event |
| ATC | Anatomical Therapeutic Classification |
| AUC | Area Under the Curve |
| C-Section | Cesarean Section |
| CRF | Case Report Form |
| CSR | Clinical Study Report |
| ECG | Electrocardiogram |
| EMA | European Medicines Agency |
| FDA | Food and Drug Administration |
| ICF | Informed Consent Form |
| ICH | International Conference on Harmonisation |
| IV | Intravenous |
| LOCF | Last Observation Carried Forward |
| MedDRA | Medical Dictionary for Regulatory Activities |
| MED | Morphine Equivalent Dose |
| n | Sample Size |
| NRS | Numerical Rating Scale |
| PACU | Post-Anesthesia Care Unit |
| PK | Pharmacokinetics |
| PO | Per Oral (by mouth) |
| PoSSe | Postoperative symptom severity questionnaire |
| SAE | Serious Adverse Event |
| SAP | Statistical Analysis Plan |
| SD | Standard Deviation |
| TEAE | Treatment-Emergent Adverse Event |
| TLFs | Tables, Listings, Figures |
| WHO-DD | World Health Organization Drug Dictionary |
| wWOCF | Windowed Worst Observation Carried Forward |

2. INTRODUCTION

This Statistical Analysis Plan (SAP) describes the planned statistical analysis and reporting of the clinical study 402-C-329 titled “A Randomized, Double-Blind, Placebo-Controlled Study to Evaluate the Safety, Efficacy, and Pharmacokinetics of Local Administration of EXPAREL for Prolonged Postsurgical Analgesia in Subjects Undergoing Third Molar Extraction”.

The structure and content of this SAP provide sufficient detail to meet the requirements identified by the US Food and Drug Administration (FDA), European Medicines Agency (EMA), and International Conference on Harmonisation (ICH) of Technical Requirements for Registration of Pharmaceuticals for Human Use: Guidance on Statistical Principles in Clinical Trials¹. All work planned and reported for this SAP will follow internationally accepted guidelines, published by the American Statistical Association² and the Royal Statistical Society³, for statistical practice.

The purposes of this SAP are to:

- Outline the types of analyses and presentations of data that will form the basis for drawing conclusions to the study objectives and hypotheses outlined in the protocol.
- Explain in detail how the data will be handled and analyzed, adhering to commonly accepted standards and practices for Good Statistical Practice.

The planned analyses identified in this SAP may be included in clinical study report (CSR), regulatory submissions, or manuscripts. Post-hoc exploratory analyses not necessarily identified in this SAP may be performed to further examine study data. Any post-hoc, unplanned, or exploratory analyses performed will be clearly identified as such in the final CSR.

The following documents related to clinical study Protocol 402-C-329 were reviewed in preparation of this SAP:

- Protocol Amendment 1 issued 27 July 2015.
- Protocol Amendment 2 issued 2 September 2015.
- Case report forms (CRFs).
- ICH Guidance on Statistical Principles for Clinical Trials (E9).
- FDA protocol feedback received 18 August 2015.

The reader of this SAP is encouraged to also read the clinical protocol and other identified documents for details on the planned conduct of this study. Operational aspects related to collection and timing of planned clinical assessments are not repeated in this SAP unless relevant to the planned analyses.

3. STUDY OBJECTIVES

The primary objective of this study is to demonstrate the analgesic efficacy of single-dose local administration of EXPAREL® (bupivacaine liposome injectable suspension) compared with placebo in subjects following bilateral third molar extraction.

The secondary objectives of this study are to assess additional efficacy parameters, characterize the pharmacokinetic (PK) profile in this surgical model, and further assess the safety profile of EXPAREL.

4. STUDY OVERVIEW

This is a Phase 3, randomized, double-blind, placebo-controlled study in subjects scheduled to undergo elective bilateral third molar extraction (i.e., extraction of all four third molars) under local anesthesia. At least one lower mandibular third molar must involve full or partial bony impaction confirmed by visual or radiographic evidence.

Approximately 175 subjects (at least 100 in the EXPAREL group and 50 in the placebo group) are planned for enrollment. Subjects enrolled under Amendment 1 were randomized in a 1:1 ratio. Due to FDA feedback Amendment 2 changed the randomization ratio to 2:1 (EXPAREL: placebo), thus subjects enrolled under Amendment 2 will be randomized in a 2:1 ratio to receive local administration of a single dose of either EXPAREL (133 mg/10 mL) or placebo (normal saline, 10 mL).

The timing of all assessments is in the Time and Events Schedule of study procedures (Section 10) and further described in the protocol.

Screening

Subjects will be screened within 30 days prior to surgery. During the screening visit, subjects will be assessed for any past or present medical conditions that in the opinion of the Investigator would preclude them from study participation.

Day 1 (Day of Surgery)

On Day 1 prior to surgery, any AEs or changes in concomitant medications since screening will be recorded, vital signs will be measured, a urine drug screen will be conducted for all subjects, and a urine pregnancy test will be conducted for women of childbearing potential. A pre-dose PK sample will be collected from all subjects eligible for randomization. Randomized subjects will receive a dental nerve block with lidocaine 2% with epinephrine 1:100,000 before undergoing bilateral third molar extraction under local anesthesia

At the end of surgery, and at least 20 minutes after the lidocaine administration, a total of 10 mL of study drug will be infiltrated [4 mL (2 mL per side) into the maxilla and 6 mL (3 mL per side) into the mandible].

Subjects will be required to remain in the research facility for 96 hours after study drug administration.

Postsurgical Safety and Efficacy Assessments

Postsurgical assessments will include pain intensity scores using the 0-10 point numeric rating scale (NRS, note that NRS assessments for this study are at rest) at scheduled timepoints and prior to each request for rescue medication; use of supplemental opioid rescue medication; vital signs; subject's satisfaction with postsurgical pain control; and the postoperative symptom severity (PoSSe) scale questionnaire (Ruta 2000).

All subjects will return for a follow-up visit on Days 7 and 10. A phone call will be made to each subject on Day 30 for an AE assessment and to inquire as to whether the subject made any unscheduled phone calls or office visits related to pain.

Adverse events will be recorded from the time the ICF is signed through Day 30. If a cardiac or neurological event occurs during the study, an unscheduled PK blood sample and ECG should be obtained within 2 hours of the time the event is noted. If there is a scheduled PK blood draw within 2 hours before or after the event, an additional draw is not needed.

Postsurgical Analgesia

Subjects should only receive rescue pain medication (oral [PO] oxycodone 10 mg) upon request for breakthrough pain, as needed. No other analgesics, including nonsteroidal anti-inflammatory drugs (NSAIDs) are allowed during the 96 hour observation period. All postsurgical opioid analgesics administered must be documented through 96 hours.

Pharmacokinetic Assessment

Blood samples for PK analysis will be obtained at baseline (prior to study drug administration); 15 minutes, 30 minutes, 1, 2, 4, 8, 12, 18, 24, 30, 36, 42, 48, 54, 60, 66, 72, 84, and 96 hours after the beginning of study drug administration; and on Days 7 and 10. Blood samples will be collected from all subjects in order to maintain the treatment double-blind. However, blood samples from subjects randomized to the placebo group will not be analyzed.

5. DEFINITIONS

Study Day

Study Day is calculated as the date of event minus the date of surgery plus one (1), if the date of event is on or after the date of surgery, thus day of surgery is Day 1. Study Day is based on the calendar dates, thus days before the date of surgery have negative values while those on or after the date of surgery are positive. However for those events that have times associated with them, if the event occurs on the day of surgery but before time 0, Study Day will be -1; Study Day will be 1 for those events occurring on the day of surgery but start after time 0.

Treatment-emergent Adverse Event

Treatment-emergent adverse events (TEAEs) are those with onset between the start datetime of study drug administration and end of study (Study Day 30 ± 3 days).

Time 0 (zero)

Time 0 is defined as the date and time of the end of surgery for all end points except AEs and bupivacaine plasma concentrations. For AEs and PK sampling times 0 is defined as the date and time of the start of study drug administration.

Pain-free

Pain-free is defined as a NRS score of 0 or 1 with no rescue medication use prior to that assessment.

Time Periods

All schedule times have a window associated with them (see [Time and Events Schedule for individual timepoint windows](#)). Various time frames are used in the data analyses which are dependent on these windows. The table below defines the actual elapsed times with allowance for the windows that can be included in the window.

| Defined time frame (hrs) | Acceptable elapsed times (hrs) |
|--------------------------|--------------------------------|
| 0-24 | [0 to 25] |
| 0-48 | [0 to 50] |
| 0-72 | [0 to 76] |
| 0-96 | [0 to 100] |
| 0-Day 10 | [0 to 264] |
| 24-48 | [23 to 50] |
| 48-96 | [46 to 100] |

If there are two or more data points that fit the time window the data point that occurs the latest in the window should be used. For example when selecting the data point for the 48 hour timepoint, if a subject has data points collected at 47 and 49 hours then the 49 hour timepoint should be used. In this example the 49 hour timepoint record will be used as the end and start of all time intervals, thus the 0-48 hour interval will end using the 49 hour record and the 48-72 hour interval will start using the same 49 hour record.

Topline Result Tables

Topline result tables are to be expedited for Pacira review after database lock. The topline tables for this study are:

- 14.1-1: Summary of Subject Disposition
- 14.2-1.1.1: Analysis of AUC of NRS Pain Intensity Scores through 48 hours – Primary Efficacy Analysis Set - Multiple Imputation Results
- 14.2-1.1.2: Sensitivity Analysis of AUC of NRS Pain Intensity Scores through 48 hours – Secondary Efficacy Analysis Set - Multiple Imputation Results
- 14.2-1.1.3: Sensitivity Analysis of AUC of NRS Pain Intensity Scores through 48 hours – Primary Efficacy Analysis Set – Mixed Model Repeated Measures Results
- 14.2-2.1: Analysis of AUC of NRS Pain Intensity Scores through 24 hours - Primary Efficacy Analysis Set - Multiple Imputation Results
- 14.2-2.2: Summary of AUC of NRS Pain Intensity Scores through 24 hours - Primary Efficacy Analysis Set - Analysis of Variance Model Results - Multiple Imputation Results
- 14.2-3.1: Analysis of AUC of NRS Pain Intensity Scores through 72 hours - Primary Efficacy Analysis Set - Multiple Imputation Results
- 14.2-3.2: Summary of AUC of NRS Pain Intensity Scores through 72 hours - Primary Efficacy Analysis Set - Analysis of Variance Model Results - Multiple Imputation Results
- 14.2-5.1: Analysis of Opioid-Free Subjects through 24 hours - Primary Efficacy Analysis Set
- 14.2-5.2: Analysis of Opioid Free Subjects through 48 hours - Primary Efficacy Analysis Set
- 14.2-5.3: Analysis of Opioid Free Subjects through 72 hours - Primary Efficacy Analysis Set
- 14.3-2.2: Summary of Potentially Clinically Meaningful Abnormal Electrocardiogram Results – Central Read - Safety Analysis Set
- 14.3-3.2: Summary of Potentially Clinically Significant Abnormal Vital Signs – Safety Analysis Set
- 14.3-4.1.2: Summary of Incidence of Treatment-Emergent Adverse Events (TEAEs) - Safety Analysis Set
- 14.3-4.2.2: Summary of Incidence of Serious Treatment-Emergent Adverse Events (TEAEs) - Safety Analysis Set

6. ANALYSIS SETS

Safety Analysis Set

The safety analysis set will include all subjects who receive study drug and will be based on the actual treatment received.

Efficacy Analysis Sets

Under the protocol, the efficacy analysis set will include all subjects in the safety analysis set who undergo the planned surgery and will be based on the randomized treatment, regardless of actual treatment received. However Amendment 2 changee the pain score collection around rescue medication use, thus subjects enrolled under Amendment 1 and Amendment 2 have differences in efficacy data collection. Subjects enrolled under Amendment 1 collected pain scores only before the first use of rescue medication while those enrolled under Amendment 2 collected pain scores prior to each use of rescue medication. This has direct impact on the derivation of the primary efficacy endpoint. Under Amendment 2 the sample size was increased to accommodate the FDA request of at least 100 subjects on EXPAREL and to ensure an adequate number of subjects in both treatment groups to enable an efficacy analyses based solely on those subjects enrolled under Amendment 2. Thus two efficacy analysis sets are defined for this study, primary and secondary efficacy analysis sets.

The primary efficacy analysis set will include all subjects enrolled under Amendment 2 in the safety analysis set who undergo the planned surgery. This will be the analysis set used for the decision on efficacy.

The secondary efficacy analysis set will include all subjects enrolled under either amendment in the safety analysis set who undergo the planned surgery. This analyses set will be used for a sensitivity analysis to ensure that the protocol amendment did not change the efficacy results. When adjusting pain scores for rescue medication use, subjects enrolled under Amendment 1 will use the highest score prior to the first rescue medication request to impute pain scores obtained in the rescue medication window.

In both efficacy analyses sets subjects will be analyzed as randomized, regardless of treatment received.

Pharmacokinetic Analysis Set

The PK analysis set will include all subjects in the safety analysis set who receive EXPAREL, provide sufficient samples to allow for calculation of PK parameters required for analysis, and do not have significant protocol deviations that may invalidate or bias the results.

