11.3. Method of Assigning Subjects to Treatment

11.3.1. Randomization Scheme

Approximately 175 subjects (100 subjects in the EXPAREL 133 mg group and 75 subjects in the placebo group) are planned for enrollment. Subjects will be randomized in a 2:1 ratio to receive local administration of a single dose of either EXPAREL (133 mg/10 mL) or placebo (normal saline, 10 mL).

The randomization code will be generated by a centralized randomization system, which will also be used to communicate subject randomizations to study sites. All randomized subjects will have both a unique subject identifier and a unique random code identifier. No subject or random code identifiers are to be reused once assigned.

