15.3. Determination of Sample Size

In previous wound infiltrations studies in hemorrhoidectomy and bunionectomy, the difference between treatment groups in mean AUC from 0 to 48 hours or NRS pain intensity scores varied from 20 to 103. The standard deviations varied from 100 to 128. A sample size of 50 in each group will have 90% power to detect a difference in means of 66 assuming that the common standard deviation is 100 using a two group t-test with a 0.05 two-sided significance level. A sample size of 50 in each group will have 90% power to detect a difference in means of 86 assuming that the common standard deviation is 130 using a two group t-test with a 0.05 two-sided significance level.

However, the EXPAREL group will randomize approximately 100 subjects to lower the AE detection threshold for the safety database to 3%. The sample size for placebo was increased due to the additional collection of NRS pain intensity score immediately prior to all requests for rescue medication through 96 hours. The placebo sample size was increased to ensure that there are at least 50 subjects treated in both the EXPAREL and placebo under the current protocol amendment. It is expected that the sample size will be approximately 175 subjects resulting in a 2:1 ratio of EXPAREL to placebo subjects.

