7.1.1. Handling Missing Values

7.1.1.1. Area Under the NRS-Time Curve

7.1.1.1.1. Multiple Imputation Method

Rubin’s (1987)⁴ multiple imputation procedure will be applied to replace each missing value with a set of plausible values that represent the uncertainty about the right value to impute. This multiple imputation method is being implemented per the advice provided in “the prevention and treatment of missing data in clinical trials”⁵ For calculation of area under the curve (AUC) of NRS pain intensity scores, the windowed worst observation carried forward (wWOCF) multiple imputation procedure will be used in the following order:

- Windowed worst observation carried forward (wWOCF) for rescue medications.

For subjects who take a rescue medication, their NRS scores recorded within the window of controlled type of rescue medication (see [Table 2](#)) will be replaced by the ‘worst’ observation. The worst observation will be the highest score from time 0.25 or end of previous rescue window, to

pain score immediately prior to rescue medication for those subjects with pain score prior to each rescue medication (Amendment 2) or, for those subjects with pain scores only prior to first rescue medication use (Amendment 1) in the time interval from time 0.25 to up to the time of rescue medication. The NRS score at rescue will be included in this

calculation. Note that NRS scores in the window that are higher than the worst value prior to rescue medication will not be overwritten.

- b) After the wWOCF imputation, described in Step a, subject data still missing with a non-monotone missing pattern (ie, all pain scores between the last non-missing score and last timepoint) will have missing scores imputed using the Markov-Chain Monte-Carlo (MCMC) method (Schafer 1997)⁶, which will be applied in the multiple imputation procedure for arbitrary missing patterns. This MCMC method will use 1000 imputation datasets with NBITER=2000 and NITER=1000.
- c) The resulting data from Step b will then have the remaining monotone missing patterns, hence a parametric regression method on pain (Rubin 1987) that assumes multivariate normality will be applied for this multiple imputation procedure.
- d) The AUC and SPIS at various time intervals will be derived from the imputed NRS scores resulting from Step c.
- e) The endpoints derived in Step d will be analyzed as described in Section 7.6.2.1 for each imputation.

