7.6.2. Methods of Analysis

7.6.2.1. Primary Efficacy Analysis

The primary efficacy analyses will be conducted for both the primary and secondary efficacy analysis sets. Results from the primary efficacy analysis set will be primary efficacy result; the analyses based on the secondary efficacy analysis set are a sensitivity analysis.

The primary efficacy variable is the AUC of NRS scores from first postsurgery assessment (0.25 hours) through 48 hours [AUC(0.25-48)] using the wWOCF to adjust for rescue medication use and multiple imputation method to account for missing data described in Section 7.1.1.1.1.

Tests for the treatment effect of EXPAREL versus placebo will be based on the following null hypothesis (H_0) and two-sided alternative hypothesis (H_a):

$H_0: \mu_s = \mu_p$ versus $H_a: \mu_s \neq \mu_p$

where μ_s and μ_p are the mean of AUC(0.25-48) for EXPAREL and the mean of AUC(0.25-48) for placebo, respectively. A two-sided test will be performed at 5% level of significance. The treatment effect of EXPAREL will be considered significantly better than that of placebo if the null hypothesis of no difference is rejected and a difference in mean of AUC(0.25-48) in favor of EXPAREL (mean for EXPAREL < mean for placebo) is observed.

For the primary efficacy variable of AUC(0.25-48), EXPAREL will be compared to placebo using analysis of variance (ANOVA) with treatment and site as main effects. Based on the model, the least squares (LS) means, LS mean difference between the two treatment groups, 95% confidence interval (CI) for the LS mean difference between the two treatment groups, and p-value will be reported.

Descriptive statistics of the primary efficacy variable will also be shown by site but no statistical analyses will be performed by site.

In addition, an ANOVA model with main effects of treatment and site and the treatment by site interaction will be reported to assess the interaction on the primary efficacy analysis. Additional analyses may be performed if the interaction effect is significant (p-value <0.05).

Sensitivity Analyses

Mixed Model Repeated Measures

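### The pooled Amendment 1 and 2 sensitivity analysis has no amendment term or contrast, so it cannot show that the amendment left efficacy unchanged

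*SAP*

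**What the plan says.** SAP Section 6 defines two efficacy sets. The primary set holds Amendment 2 subjects and carries the efficacy decision. The secondary set holds subjects from both amendments, and its purpose is given as: "This analyses set will be used for a sensitivity analysis to ensure that the protocol amendment did not change the efficacy results".

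The amendments differ in two ways that matter here.

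- **Allocation.** SAP Section 4 states: "Subjects enrolled under Amendment 1 were randomized in a 1:1 ratio". Under Amendment 2 the ratio is 2:1.
- **Endpoint derivation.** Amendment 1 collected a pain score only before the first rescue; Amendment 2 collects one before every rescue. Of this change SAP Section 6 says: "This has direct impact on the derivation of the primary efficacy endpoint". For the worst-score replacement, "subjects enrolled under Amendment 1 will use the highest score prior to the first rescue medication request", whereas Amendment 2 subjects use the scores since the previous rescue window ended.

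For the primary endpoint, on both sets, SAP 7.6.2.1 says "EXPAREL will be compared to placebo using analysis of variance (ANOVA) with treatment and site as main effects". The shell footnote reused for Table 14.2-1.1.2 and the Section 12 code give the same model. The only treatment interaction planned in the AUC ANOVA is treatment by site.

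The historical single-imputation analysis (SAP 7.1.1.1.2) applies one look-back to everyone. SAP 7.6.2.1 plans it for both sets with treatment as the only effect, but the shells list its table (14.2-1.1.5) for the primary set only.

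**The concern.** Table 14.2-1.1.2 is on the topline list and is meant to give reassurance about the amendment. Because the primary set is nested in the pooled set, the two results will tend to agree whatever happened under Amendment 1. A reader could take that agreement as evidence that the amendment had no effect when nothing planned tests it.

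A smaller issue follows from the changed allocation. Amendment 1 subjects form a larger share of the placebo arm than of the EXPAREL arm. If mean AUC differs between amendments, because of the look-back rule or for any other reason, part of that difference enters the pooled treatment difference.

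**Working it through.** **The plan's own figure.** Protocol 15.3 gives 90% power with 50 per group for a difference of 66 at SD 100, or 86 at SD 130 (two-sided 0.05). The noncentrality is 66/(100 x sqrt(2/50)) = 3.30 and 86/(130 x sqrt(2/50)) = 3.31, on 98 df. Power is 90.4% and 90.6%, so both reproduce. SD 100 and a difference of 66 are used below.

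**Assumed splits.** The stated figures cannot all hold at once. With exact 1:1 and 2:1 phases and the Protocol 11.3.1 totals ("100 subjects in the EXPAREL 133 mg group and 75 subjects in the placebo group"), let x be Amendment 1 subjects per arm and y Amendment 2 placebo subjects. Then x + 2y = 100 and x + y = 75, so y = 25 and x = 50. But Protocol 15.3 wants "at least 50 subjects treated in both the EXPAREL and placebo under the current protocol amendment". Three splits of 175 are therefore shown, each missing one stated figure.

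| | A | B | C |
|---|---|---|---|
| Amendment 1, EXPAREL:placebo | 12.5:12.5 | 25:25 | 50:50 |
| Amendment 2, EXPAREL:placebo | 100:50 | 75:50 | 50:25 |
| Overall | 112.5/62.5 | 100/75 | 100/75 |
| Figure not met | 100/75 overall | 2:1 (is 1.5:1) | 50 placebo under Amendment 2 (is 25) |

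**Can the pooled table detect a change?** SE = 100 x sqrt(1/nE + 1/nP). For nested sets, the correlation of the two treatment differences is pooled SE / primary SE. If the effect is -66 under Amendment 2 and 0 under Amendment 1, the pooled result is -66 x (Amendment 2 share of EXPAREL). Its chance of p<0.05 is Φ(size/SE - 1.96).

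| | A | B | C |
|---|---|---|---|
| Primary set / pooled set | 150/175 = 86% | 125/175 = 71% | 75/175 = 43% |
| Primary SE; pooled SE | 17.3; 15.8 | 18.3; 15.3 | 24.5; 15.3 |
| Correlation | 0.91 | 0.84 | 0.62 |
| Pooled result | -58.7 | -49.5 | -33.0 |
| Chance of p<0.05 | 96% | 90% | 58% |

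**Bias from a shift common to both arms.** With treatment only, the fraction of the shift that enters is the Amendment 1 share of placebo minus its share of EXPAREL.

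- A: 12.5/62.5 - 12.5/112.5 = 8.9%
- B: 25/75 - 25/100 = 8.3%
- C: 50/75 - 50/100 = 16.7%

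The maximum over all splits with exact ratios is 17.2%, at 49% Amendment 1. The bias favours EXPAREL if Amendment 1 AUCs are higher and goes against it if they are lower.

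With site in the model, assume all Amendment 1 subjects are at one of the three sites named in the addendum shells (100, 200, 300) and Amendment 2 enrolment is equal across sites. Weighting sites by nE x nP/(nE + nP) gives 6.9%, 5.3% and 7.9%. The bias is zero if no site enrolled under both amendments.

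As an illustration, take a shift of 1 NRS point at 12, 24 and 48 h in every subject. The trapezoid weights are 8 + 18 + 12 = 38 units. Without site adjustment the bias is 3.4, 3.2 and 6.3 units, or 0.2 to 0.4 of the pooled SE.

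**The sign of a look-back shift is not known.** Take rescues at 1 h and 10 h with 6-hour windows, so that only the 12 h score (weight 8 h) differs.

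- Score 8 before the first rescue and 4 before the second: the Amendment 1 rule gives (8 - 4) x 8 = 32 units more.
- Highest score 4 up to the first rescue and 7 before the second: it gives (7 - 4) x 8 = 24 units less.

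**Precision of the missing contrast.** The SE of the difference between the amendment-specific effects is sqrt(SE1² + SE2²).

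| | A | B | C |
|---|---|---|---|
| Amendment 1 SE; Amendment 2 SE | 40.0; 17.3 | 28.3; 18.3 | 20.0; 24.5 |
| Contrast SE | 43.6 | 33.7 | 31.6 |
| 95% CI half-width | 85 | 66 | 62 |
| Power for 66 units | 33% | 50% | 55% |

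**The case against.** The strongest reply is that this concerns one over-strong verb in an analysis that decides nothing.

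- **The pooled set is legitimate.** It is the protocol's own efficacy set (Protocol 15.4), so it is reasonable to show whether restricting to Amendment 2 alters the conclusion.
- **The size is overstated.** Exact 2:1 allocation with at least 50 placebo under Amendment 2 needs 150 subjects, leaving about 25 of 175, which is split A. Split C and the 17.2% ceiling break that minimum. Where the bias is largest (C), the masked result halves to -33.0, which a reader would notice.
- **The shift is hypothetical.** The look-back rules differ only for later rescues, so only subjects rescued more than once could be affected by the rule change. A shift of 38 units in every subject is close to a worst case.
- **Amendment 1 results are recoverable.** Arm means follow approximately by subtracting the two nested tables, and the listings give set membership, AUC and protocol version.
- **The common-rule analysis is planned on the secondary set**, and the suggested contrast is too imprecise to prove anything.

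Much of this stands. Split A fits the stated constraints best, the bias is slight, and the primary decision is untouched. But means obtained by subtraction give neither an adjusted estimate nor an interval. The historical analysis has no amendment term, no contrast and no listed secondary-set table. The weakness of the contrast is itself a reason not to claim that the pooled table ensures anything.

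**Conclusion.** The concern holds and is minor. The nesting argument needs no assumed split: without an amendment term or contrast, agreement between the primary and pooled tables cannot establish that the amendment left efficacy unchanged. Under split A a complete loss of effect in Amendment 1 would move the result only from -66 to -58.7.

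The possible bias is a lesser matter: 8.9% of any shift in split A without site (6.9% with site, under the assumed layout), and 8.3% and 16.7% in B and C. It rests on assumed splits, an unestablished shift of unknown sign, and site layout.

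The efficacy decision and the secondary endpoints use Amendment 2 subjects only and are unaffected. The text available for this check lacked a passage after the Section 12 code and a passage of the addendum between its Purpose section and the per-protocol table list, so the conclusion covers the remaining text.

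**What to change.** 1. Add amendment as a factor in the secondary-set ANOVA for Table 14.2-1.1.2: SAP 7.6.2.1, the shell footnote and the Section 12 code. Listing 16.2-20 already carries protocol version, so the factor should be derivable.
2. Add it to the treatment-only historical ANOVA on the secondary set, and add the missing secondary-set shell.
3. In both, report the treatment difference within each amendment and their contrast with 95% CIs, labelled as imprecise. Read the contrast beside the common-rule historical result, because an amendment main effect does not remove a look-back artefact if rescue use differs by arm.
4. Reword SAP Section 6 so that the pooled analysis describes results in all treated subjects who had the planned surgery, without claiming to ensure no amendment effect.
5. Clarify SAP 7.1.1.1.1 step a. Its Amendment 1 wording, "Amendment 1) in the time interval from time 0.25 to up to the time of rescue medication", can mean the first rescue, as in Section 6, or each rescue.

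The cost is one or two model terms, a few table rows and one shell. At SD 100 the SE of the pooled difference goes from 15.8 to 15.9 (A), stays at 15.3 (B), and goes from 15.3 to 15.5 (C). An additive amendment shift then no longer biases the estimate. The contrast would still not prove the absence of an amendment effect.
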